1.3.1 Study Design Rationale

This is a double-blind, randomized, multicenter, outpatient evaluation of the safety and efficacy of rimegepant as compared to placebo in the treatment of moderate or severe migraine. The study drug will be rimegepant formulated in a 75 mg ODT (administered sublingually) or a matching placebo. The subjects will be instructed to take their study medication, as an outpatient, when (if) they have a migraine headache which reaches moderate or severe intensity.

The study will randomize approximately 1430 subjects. The subjects will be randomized in a 1:1 ratio to the rimegepant or placebo treatment groups. The randomization will be stratified by the use of prophylactic migraine medications (yes or no).

This study design is utilized to confirm the efficacy and safety profiles observed in the Phase 2b study with rimegepant. Incorporation of placebo and use of appropriate rescue medications will permit enrollment of subjects with a broad range of comorbidities, including cardiovascular conditions, representative of the potential treatment population.

1.3.2 Dose Selection Rationale

Study CN170003 was a double-blind, randomized, placebo-controlled, dose-ranging trial of rimegepant for the acute treatment of migraine [7]. The primary objective was to evaluate the efficacy of rimegepant compared with placebo in the acute treatment of migraine as measured by pain freedom (head pain intensity level reported as “no pain”) at 2 hours post-dose using a four point rating scale (no pain, mild pain, moderate pain, severe pain) while identifying an optimal dose to support the Phase 3 clinical trials. Subjects were randomized to receive placebo, sumatriptan 100 mg or rimegepant (10, 25, 75, 150, 300, or 600 mg). Randomization made use of an adaptive design, whereby one quarter of subjects were assigned placebo and one-eighth were assigned sumatriptan; the remainder were assigned to one of the six rimegepant groups based on a Bayesian analysis of the observed response rates. Subjects were instructed to treat one migraine of moderate or severe pain intensity and return to the clinic within 7 days.

A total of 885 subjects were randomized and 812 completed the study. Key entry criteria were very similar to those chosen for this clinical trial.

A comprehensive and durable efficacy profile for rimegepant was demonstrated to be fully present at 75 mg but not at lower doses (i.e., 10 mg or 25 mg). This dose was selected as the optimal dose to support Phase 3 clinical trials, given that larger doses (150 mg, 300 mg, 600 mg) showed a similar efficacy profile and there was no pattern of added

benefit in dosing higher, consistent with previously published migraine studies[8]. rimegepant at 75 mg showed statistically significant broad efficacy across all four traditional endpoints at 2 hr (pain, nausea, photophobia and phonophobia) which was durable and persisted through 24 hr. At 2 hr following a single oral dose of 75 mg, subjects who previously were experiencing moderate-to-severe migraine pain had no-pain (31.4% p = 0.0018) or mild-to-no-pain (72.1%) as compared to placebo (15.3% and 51.2%, respectively). For the 75 mg dose at 2 hr, subjects also showed significant freedom from nausea (67.4%, p = 0.0074) freedom from phonophobia (52.3%, p = 0.0001) and freedom from photophobia (41.9%, p = 0.0023) vs. placebo (51.2%, 28.1% and 24.1%, respectively). The lasting nature of these beneficial anti-migraine effects were evidenced by a comparatively similar efficacy profile in the 2-24 hr measures, where rimegepant at 75 mg produced significant 2-24 hr sustained pain freedom (27.9%, p < 0.0001) and 2-24 hr sustained pain relief (69.8%, p < 0.0001) vs. placebo (7.4% and 42.4%, respectively).

1.3.3 Other Rationale related to the compound/study

Prior to initiation of this study, a Phase 1 crossover study will be conducted in healthy volunteers to assess the pharmacokinetic comparability of a single dose of the rimegepant ODT with the previously studied rimegepant tablet. This information will be incorporated in a future version of the Investigator Brochure.

1.4 Research Hypothesis

Rimegepant will have efficacy superior to placebo in the treatment of acute migraine with a favorable safety profile suitable for use by a broad subject population.

2 STUDY OBJECTIVES

2.1 Primary

To evaluate the efficacy of rimegepant compared with placebo in the acute treatment of migraine as measured by the co-primary endpoints of **pain freedom** and **freedom from the most bothersome symptom (MBS)**, associated with migraine, at two hours post dose.

2.2 Secondary

- 1) To evaluate rimegepant compared to placebo on **pain relief at 2 hours** post-dose
 - 2) To evaluate the effect of rimegepant relative to placebo on the ability to **function normally at 2 hours** post-dose as reported on the Functional Disability scale.
 - 3) To evaluate rimegepant compared to placebo on **sustained pain relief from 2 to 24 hours** post-dose
 - 4) To evaluate rimegepant compared to placebo on **sustained freedom from the most bothersome symptom**, associated with migraine, **from 2 to 24 hours** post-dose.
 - 5) To evaluate rimegepant compared to placebo on the **probability of requiring rescue medication** within 24 hours of initial treatment
 - 6) To evaluate rimegepant compared to placebo on the **sustained ability to function at a normal level**, as measured by the functional disability scale, **from 2 to 24 hours** post-dose.
 - 7) To evaluate rimegepant compared to placebo on **sustained pain relief from 2 to 48 hours** post-dose
 - 8) To evaluate rimegepant compared to placebo on **freedom from the most bothersome symptom**, associated with migraine, **from 2 to 48 hours** post-dose.
 - 9) To evaluate rimegepant compared to placebo on the **sustained ability to function at a normal level**, as measured by the functional disability scale, **from 2 to 48 hours** post-dose.
 - 10) To evaluate rimegepant compared to placebo on **freedom from photophobia** at 2 hours post-dose
 - 11) To evaluate the effect of rimegepant relative to placebo on the ability to **function at a “normal” level at 90 minutes** post-dose as reported on the Functional Disability scale
 - 12) To evaluate rimegepant compared to placebo on **pain relief at 90 minutes** post-dose
-

- 13) To evaluate rimegepant compared to placebo on **sustained pain freedom from 2 to 24 hours** post-dose
- 14) To evaluate rimegepant compared to placebo on **freedom from the most bothersome symptom**, associated with migraine, **at 90 minutes** post-dose.
- 15) To evaluate rimegepant compared to placebo on **pain freedom at 90 minutes** post-dose
- 16) To evaluate rimegepant compared to placebo on **freedom from phonophobia** at 2 hours post-dose
- 17) To evaluate rimegepant compared to placebo on **sustained pain freedom from 2 to 48 hours** post-dose
- 18) To evaluate rimegepant compared to placebo on **pain relief at 60 minutes** post-dose
- 19) To evaluate the effect of rimegepant relative to placebo on the ability to **function at a “normal” level at 60 minutes** post-dose, as reported on the Functional Disability scale.
- 20) To evaluate rimegepant compared to placebo on **freedom from nausea** at 2 hours post-dose
- 21) To evaluate rimegepant compared to placebo for the incidence of **pain relapse** from 2 to 48 hours post-dose

2.3 Exploratory

- To evaluate the effect of rimegepant relative to placebo on the subjects ability to work or function at 24 hrs post dose according to the Functional Disability scale
 - To evaluate rimegepant compared to placebo on **pain relief at 30 minutes** post-dose
 - To evaluate rimegepant compared to placebo on **pain relief at 15 minutes** post-dose
 - To evaluate the effect of rimegepant relative to placebo on the **Migraine Preference of Medication (PoM)**
-

- To evaluate rimegepant relative to placebo for pain relief on the 4 point scale at all scheduled time points post dose
 - To evaluate the effect of rimegepant relative to placebo on the **Migraine Quality of Life (MQoLQ)**
 - To evaluate the **tolerability and safety** of rimegepant in the acute treatment of migraine as measured by the frequency of adverse events of at least moderate intensity, serious adverse events; and clinically relevant laboratory abnormalities
 - To evaluate the effect of rimegepant relative to placebo on the **Sheehan Suicidality Tracking Scale**
-

3 STUDY ENDPOINTS

3.1 Primary

Pain freedom will be assessed using the number of evaluable subjects that report no pain at 2 hours post-dose. Pain will be measured on a 4 point Likert scale (0=none, 1=mild, 2=moderate, 3=severe).

Freedom from the most bothersome symptom (MBS) will be assessed using the number of evaluable subjects that report the absence of their MBS at 2 hours post-dose. The MBS (nausea, phonophobia or photophobia) will be measured using a binary scale (0=absent, 1=present).

3.2 Secondary

- 1) **Pain Relief at 2 hours** post-dose, will be assessed using the number of subjects that report a pain level of moderate or severe at baseline and then report a pain level of none or mild at two hours post-dose.
 - 2) The proportion of subjects able to **function normally, at 2 hours** post-dose, will be assessed using the number of subjects that self-report as “normal” on the Functional Disability scale.
 - 3) **Sustained pain relief, from 2 to 24 hours** will be assessed using the number of subjects that do not use any rescue medications, and do not experience any moderate or severe headache pain through the time period of interest.
 - 4) **Sustained freedom from the most bothersome symptom, from 2 to 24 hours**, will be assessed using the number of subjects that do not experience their most bothersome symptom through the time period of interest.
 - 5) The **probability of requiring rescue medication** will be assessed using the number of subjects that take rescue medication within 24 after administration of study medication (rimegepant or placebo).
 - 6) **Sustained ability to function at a normal level, from 2 to 24 hours**, will be assessed using the number of subjects that self-report as “normal” on the Functional Disability scale through the time period of interest.
-

- 7) **Sustained pain relief from 2 to 48 hours**, will be assessed using the number of subjects that do not use any rescue medications, and do not experience any moderate or severe headache pain through the time period of interest.
 - 8) **Sustained freedom from the most bothersome symptom, from 2 to 48 hours**, will be assessed using the number of subjects that do not experience their most bothersome symptom through the time period of interest.
 - 9) **Sustained ability to function at a normal level, from 2 to 48 hours**, will be assessed using the number of subjects that self-report as “normal” on the **functional disability** scale through the time period of interest.
 - 10) **Freedom from photophobia** will be assessed by tabulating the number of subjects that report the absence of photophobia at 2 hours post-dose in the subset of subjects that reported the presence of photophobia at headache baseline.
 - 11) The proportion of subjects able to **function normally, at 90 minutes** post-dose, will be assessed using the number of subjects that self-report as “normal” on the functional disability scale.
 - 12) **Pain relief at 90 minutes** post-dose, will be assessed using the number of subjects that report a pain level of moderate or severe at baseline and then report a pain level of none or mild at 90 minutes post-dose.
 - 13) **Sustained pain freedom, from 2 to 24 hours**, will be assessed using the number of subjects that do not experience any headache pain through the time period of interest.
 - 14) **Freedom from the most bothersome symptom (MBS)** will be assessed using the number of evaluable subjects that report the absence of their MBS **at 90 minutes** post-dose.
 - 15) **Pain freedom** will be assessed using the number of evaluable subjects that report no pain **at 90 minutes** post-dose.
 - 16) **Freedom from Phonophobia** will be assessed by tabulating the number of subjects that report the absence of phonophobia at 2 hours post-dose in the subset of subjects that reported the presence of phonophobia at headache baseline.
-

- 17) **Sustained pain freedom, from 2 to 48 hours**, will be assessed using the number of subjects that do not experience any headache pain through the time period of interest.
- 18) **Pain Relief at 60 minutes** post-dose, will be assessed using the number of subjects that report a pain level of moderate or severe at baseline and then report a pain level of none or mild at 60 minutes post-dose.
- 19) The proportion of subjects able to **function normally, at 60 minutes** post-dose, will be assessed using the number of subjects that self-report as “normal” on the functional disability scale.
- 20) **Freedom from Nausea** will be assessed by tabulating the number of subjects that report the absence of nausea at 2 hours post-dose in the subset of subjects that reported the presence of nausea at headache baseline.
- 21) **Pain relapse** will be assessed using the number of subjects that are pain free at 2 hours post-dose and then have a headache of any severity (response of 1, 2 or 3 on the 4 point scale) within 48 hours after administration of study medication (BHV3000 or placebo).

3.3 Measures of Interest

Safety and Other assessments:

[figure not shown]
- Adverse Events
 - ECG assessments
 - Vital Sign and Physical Measurements
 - Routine Laboratory Tests
 - Sheehan Suicidality Tracking Scale (S-STTS)
 - Preference of Medication (PoM)
 - Assessment of Migraine Pain and Symptoms
 - Migraine Specified Quality of Life Questionnaire (MQoLQ)
-

4 STUDY PLAN

4.1 Study Design and Duration

This is a double-blind, randomized, multicenter, outpatient evaluation of the safety and efficacy of rimegepant as compared to placebo in the treatment of moderate or severe migraine. Subjects will be dispensed one dose of study medication consisting of a rimegepant 75 mg ODT (administered sublingually) or a matching placebo. The total duration of the study will be approximately 11 weeks. This includes a 3-28 day Screening Period, an Acute Phase that can last up to 45 days or until the subject has a migraine that reaches moderate or severe intensity, followed by an End of Treatment Visit 7 days after the administration of the study medication.

4.2 Study Schematic

4.3 Schedule of Assessments

Table 1: Schedule of Assessments

| Procedure | Screening Visit (3-28 days)¹ | Baseline Visit (Randomization)¹ | Onset of moderate or severe migraine² | During Treatment 15, 30, 45, 60 and 90 minutes Post-Dose | During Treatment 2, 3, 4, 6, 8 hours Post- Dose | During Treatment 24 hours Post-Dose | During Treatment 48 hours Post- Dose | End of Treatment Visit (within 7 days of migraine)¹⁵ |
|--|--|---|---|---|--|--|---|--|
| Eligibility Assessments | | | | | | | | |
| Informed Consent | X | | | | | | | |
| Inclusion/Exclusion Criteria | X | X | | | | | | |
| Medical History | X | | | | | | | |
| Prophylactic Migraine Medication/ Concomitant Medication ³ | X | X | | | | | | X |
| Assessment of Migraine History (Signs and symptoms) paper source ¹⁴ | X | | | | | | | |

| Procedure | Screening Visit (3-28 days)¹ | Baseline Visit (Randomization)¹ | Onset of moderate or severe migraine² | During Treatment 15, 30, 45, 60 and 90 minutes Post-Dose | During Treatment 2, 3, 4, 6, 8 hours Post-Dose | During Treatment 24 hours Post-Dose | During Treatment 48 hours Post-Dose | End of Treatment Visit (within 7 days of migraine)¹⁵ |
|---|--|---|---|---|---|--|--|--|
| Safety Assessments | | | | | | | | |
| Physical Examination | X | | | | | | | X |
| Vital Signs/Physical Measurements ⁴ | X | X | | | | | | X |
| Clinical Safety Laboratory Testing ⁵ | X | | | | | | | X |
| Urine drug screen for drugs of abuse | X | | | | | | | X |
| ECG | X | | | | | | | X |
| Pregnancy Test ⁶ | X | X | X | | | | | X |
| Adverse Event and Serious Adverse Event Assessment ⁷ | X | X | X | X | X | X | X | X |
| Sheehan Suicidality Tracking Scale ⁸ | X | X | | | | | | X |

| Procedure | Screening Visit (3-28 days)¹ | Baseline Visit (Randomization)¹ | Onset of moderate or severe migraine² | During Treatment 15, 30, 45, 60 and 90 minutes Post-Dose | During Treatment 2, 3, 4, 6, 8 hours Post-Dose | During Treatment 24 hours Post-Dose | During Treatment 48 hours Post-Dose | End of Treatment Visit (within 7 days of migraine)¹⁵ |
|---|--|---|---|---|---|--|--|--|
| Efficacy Assessments¹² | | | | | | | | |
| Assessment of migraine pain ¹³ | | | X | X | X | X | X | |
| Assessment of Migraine Symptoms (photophobia, phonophobia, and nausea - eDiary) ¹³ | | | X | X | X | X | X | |
| Functional Disability Scale ¹³ | | | X | X | X | X | X | |
| MQoLQ (Migraine Specified Quality of Life Questionnaire) ¹³ | | | | | | X | | |
| Preference of Medication ¹³ | | | | | | X | | |

¹ **Screening Phase** will be 3 - 28 days. The **Baseline Visit** may be scheduled but should only occur *after* all screening procedures are complete, subject meets inclusion/exclusion criteria, and lab test results have been received by the site.

² Subjects will use eDiary to answer questions about their migraine symptoms upon experiencing a moderate/severe migraine headache. The subject will administer pre-dispensed study drug if 1) the headache remains moderate or severe; 2) the subject has completed all required migraine assessment questions in the eDiary, including their current most bothersome migraine symptom, and 3) the subject has not already taken prohibited medications (see protocol section 5.4).

³ Subjects should keep track of their concomitant medications throughout the study and report them to the study personnel at the End of Treatment Visit. Any medication taken for recurrent headache should be documented. Use of concomitant medications after randomization, including rescue medications, will be recorded by the subject on a paper diary and reported to the site.

⁴ Height will only be captured at the Screening Visit. Weight, body temperature, respiratory rate, blood pressure and heart rate will be collected at all time points where indicated. Sitting arterial systolic and diastolic blood pressure and pulse rate will be measured.

⁵ **Screening Visit:** All screening visit laboratory test results must be received prior to Baseline (randomization) Visit.

⁶ A serum pregnancy test will be completed at Screening and End of Treatment Visits as part of the standard laboratory tests (if appropriate). Confirmatory urine pregnancy test for WOCBP should be completed on site at Baseline Visit and any subsequent visits for confirmation at the Investigator's discretion. Home pregnancy test will be provided to WOCBP after completion of baseline visit. WOCBP subjects must complete the urine pregnancy test at home prior to taking study medication.

⁷ SAEs are reported from the time of informed consent and non-serious AEs are reported from baseline. All ongoing non-serious AEs and SAEs will be followed to resolution or until investigator deems there will be no further status change. SAEs that occur during the treatment period should be reported to site in real time. Non-serious AEs that occur during the treatment period should be reported to the site at the EOT.

⁸ This scale will be clinician administered, completed on site, and will be in paper. The source document will be provided by Biohaven. The assessment period for completing the scale will be 30 days prior to Screening, and since the last visit for the remainder of the study.

⁹ Subjects will be randomized in the IWRS system at the Baseline Visit (Randomization Day 01).

¹⁰ Subjects should be instructed that the dose should be taken once the migraine attack reaches moderate or severe pain and after the subject has completed all required migraine assessments in the eDiary. The eDiary will prompt the subject to take study medication.

¹¹ Site staff to review and confirm entries with subjects and confirm all data points are transferred to the system and reset eDiary for future subject use, PRIOR to the subject leaving the clinic.

¹² ± Windows for timeframe around efficacy assessments (15, 30, 45, 60, 90 min, 2, 3, 4, 6, 8, 24 and 48 hours) will be automated and captured in the eDiary.

¹³ These scales will be captured in the eDiary. Subjects will also be asked about their most bothersome symptom at the time of reporting and treating a qualifying migraine.

¹⁴ Paper source document will be used to capture Migraine History. Subjects will also be asked about their typical most bothersome symptom when having a migraine.

¹⁵ Subjects should return to the site for their EOT visit within 7 (+2) days from their migraine occurring.

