4.9.3 Laboratory Data

Clinical laboratory evaluations include:

Hematology: hemoglobin, hematocrit, red blood cell count, white blood cell count with differential, and platelets

Serum Chemistry: sodium, potassium, chloride, bicarbonate, calcium, glucose, BUN (urea), serum creatinine, uric acid, ALT, AST, alkaline phosphatase, LDH, total protein, albumin, total bilirubin, direct bilirubin, indirect bilirubin, CPK (with fractionation, if available)

Lipid Panel: Cholesterol, LDL, HDL, triglycerides (screening only)

Estimated glomerular filtration rate (eGFR) using the estimated modification of diet in renal disease (MDRD) formula will be calculated and reported by the central lab at each visit that the clinical laboratory test is collected.

Urinalysis: pH, specific gravity, protein, ketones, nitrites, urobilinogen, leukocyte esterase, protein, glucose, microalbuminuria, and blood. If blood, protein, or leukocytes are positive, reflex to microscopic examination.

Urine drug screen: for drugs of abuse

Clinical laboratory values will be expressed using both Standard US units and SI units. Tabulations, listings, and graphics will be provided to show the data in both systems, unless specified otherwise.

The observed value and change from baseline will be summarized for select continuous laboratory parameters at baseline and the end of treatment visit. In addition, the shift from baseline in laboratory tests will be summarized as the number and percentage of subjects with each category (low, normal, high) at baseline and the end of treatment visit. Note that shift

categories are independent of US and SI units. For AST and ALT, the shift tables will use the following categories (SI and US units are the same): Normal, >ULN, >3x ULN, and >5x ULN. In the event of repeat values from the same post-baseline visit, the non-missing value closest to the target date for the visit will be used. In the case of a tie, the latest record will be used.

All laboratory data will be provided in by-subject listings that indicate which values are on study or on treatment. Additional listings will be presented for all abnormal laboratory values.

On-study laboratory values are those with collection date/time after the randomization date/time.

On-treatment laboratory values are those with collection date/time after the first dose of study drug date/time. (Thus, on-treatment laboratory values are a subset of on-study values.)

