These definitions of on-study/on-treatment apply to vital signs, physical measurements, ECGs, and suicidal ideation and behaviors.

4.9.3.1 *Liver Toxicity Evaluation*

Potential drug induced liver injury (DILI) are those events meeting Hy's Law, defined as:

1. Aminotransferases (AT) ALT or AST elevation > 3 times the upper limit of normal (ULN);
2. Total bilirubin (TBL) > 2 times ULN, without initial findings of cholestasis (elevated serum alkaline phosphatase); and
3. No other immediately apparent possible causes of AT elevation and hyperbilirubinemia, included but not limited to: viral hepatitis, pre-existing chronic or acute liver disease, or the administration of other drug(s) known to be hepatotoxic.

Any on-study potential DILI, meeting the above defined criteria, will be reported as SAEs in the SAE summary table (see [Section 4.9.2](#)). A by-subject listing of potential DILI will be prepared that shows the AT and TBL values for all subjects that experience either AT > 3 times the upper limit of normal or TBL > 2 times the upper limit of normal at any time.

Additionally, a table will be created that summarizes the on-study incidence (as the number and percentage of subjects with an elevation) of the following:

- >3x, >5x, >10x, and >20x ULN elevations of AST, ALT, and either ALT or AST
- Any elevations of bilirubin >1x ULN and >2x ULN
- Any elevations of ALP > 1.5x ULN
- Elevation of AST or ALT (>3x ULN) accompanied by elevated bilirubin (>1.5x ULN and >2x ULN)

- Elevation of AST or ALT along with an on-study AE of nausea, vomiting, anorexia, abdominal pain, or fatigue

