4.9.7 Sheehan-Suicidality Tracking Scale (S-STS)

The S-STS is a prospective, self-reported rating scale that contains 16 questions to track both treatment-emergent suicidal ideation and behaviors. In the event the subject is unavailable, the S-STS clinician-administered rating scale will be completed that contains 6 yes/no questions.

Self-reported S-STS scores are calculated as follows:

Ideation subscale score: Sum of scores (0 – 4) for Questions 2 – 11

Behavior subscale score: Sum of scores (0 – 4) for Questions 1a, (highest of 12 or any row of 16), (highest of 14 or any row of 15), 17, and 20

Total score: Sum of the ideation and behavior subscale scores

The self-reported S-STS ideation subscale, behavior subscale, and total score will be summarized at baseline, and the number and percentage of subjects in change from baseline categories (i.e., <-1 , -1 , no change, 1 , >1) will be summarized at the end of treatment visit.

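### SAP 4.9.3 labels the End of Treatment suicidality score on-treatment, although its recall period can include up to 45 days before the single dose

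*Protocol*

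**What the plan says.** Protocol 4.3, Table 1, schedules the S-STS at Screening, Baseline (randomization) and End of Treatment, with nothing at dosing. Footnote 8 defines the recall as "30 days prior to Screening, and since the last visit for the remainder of the study". SAP Appendix 2 repeats both.

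Protocol 4.1 describes "an Acute Phase that can last up to 45 days or until the subject has a migraine that reaches moderate or severe intensity". Footnote 15 of Table 1 adds: "Subjects should return to the site for their EOT visit within 7 (+2) days from their migraine occurring".

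SAP 4.9.3 says: "On-treatment laboratory values are those with collection date/time after the first dose of study drug date/time". It then extends the rule: "These definitions of on-study/on-treatment apply to vital signs, physical measurements, ECGs, and suicidal ideation and behaviors". SAP 4.9 requires the by-subject safety listings to show which values are on-study or on-treatment. It sets the safety baseline at the last value on or before randomization.

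SAP 4.9.7 describes the scale's purpose as to "track both treatment-emergent suicidal ideation and behaviors". It plans counts and percentages of subjects in five change-from-baseline categories at End of Treatment. SAP Appendix 1 places these in Table 14.5.4, for treated subjects.

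Adverse events are handled differently. SAP 4.9.2 classes each one by its own start date relative to the first dose.

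**The concern.** A blood sample or an ECG describes the moment at which it is taken, so collection after the dose is a sound test of whether the value is on-treatment. A recall scale describes an interval. At End of Treatment that interval starts at randomization and includes all of the wait for a qualifying migraine. A subject whose ideation came and went in that wait, and who then took the tablet, gets an on-treatment flag in the listing and a positive change in Table 14.5.4.

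Both documents list the effect of rimegepant on the S-STS as an exploratory objective. The protocol uses no data and safety monitoring committee (Protocol 10.2), so interpretation of these few events rests on the listings and this table. A score above 0 is an exclusion criterion (Protocol 5.3, item 6f), so almost any non-zero End of Treatment score will appear as an increase. Nothing in the plan records on which side of the dose it fell.

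**Working it through.** **Inputs**
- Wait from Baseline to dose, *t*: 0 to 45 days (Protocol 4.1).
- Dose to End of Treatment, *d*: 7 days, or 9 with the window (Table 1, footnote 15). SAP Table 6 accepts any visit later than the day of dose + 2, so *d* can be as short as about 3.
- Eligible rate of moderate or severe attacks: 2 to 8 per month (Protocol 5.2, items 2c and 2e).
- Planned share with a migraine in the period: roughly 85% (Protocol 9.2, SAP 4.1).

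**Check of the visit intervals.** (28 + 45 + 7)/7 = 11.4 weeks, which agrees with the stated duration of about 11 weeks.

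**Largest pre-dose share of the recall period**, *t*/(*t* + *d*):
- *d* = 7: 45/52 = 87%
- *d* = 9: 45/54 = 83%
- *d* = 3: 45/48 = 94%

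Pre-dose time exceeds post-dose time only when *t* > *d*.

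**Typical share.** The documents give no distribution for the wait. *Assumption:* exponential time to the first qualifying attack, that attack is treated, truncated at 45 days, with rate λ = attacks per month/30. The mean per-subject share is the integral from 0 to 45 of [*t*/(*t* + *d*)] λ exp(−λ*t*)/(1 − exp(−45λ)) d*t*.

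| Attacks per month | Dosed by day 45 | Mean wait (days) | Mean share, *d* = 7 | Mean share, *d* = 3 | Mean share, *d* = 9 | Subjects with *t* > 7 |
|---|---|---|---|---|---|---|
| 2 | 95% | 12.6 | 53% | 69% | 48% | 61% |
| 4 | 99.8% | 7.4 | 42% | 58% | 37% | 39% |
| 8 | >99.9% | 3.7 | 29% | 45% | 25% | 15% |

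Setting λ from the 85% planning figure gives −ln(0.15)/45 = 0.0422 per day, a mean wait of 15.8 days and a mean share of 59% (*d* = 7). But 0.0422 × 30 = 1.26 attacks per month, below the entry minimum of 2, so I do not rest the size on it.

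**Effect on the comparison between arms.** *Assumptions, for illustration only:* background of 0.5% of subjects per 7 days, post-dose risk ratio 3, 600 per arm, *d* = 7, rare events. Then p(placebo) = (0.005/7)(*t* + 7), p(rimegepant) = (0.005/7)(*t* + 21), and SE = √[Σp(1 − p)/600].

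| Wait | Placebo | Rimegepant | Difference | SE of difference | Ratio |
|---|---|---|---|---|---|
| Post-dose period only | 0.50% | 1.50% | 1.0 point | 0.57 | 3.0 |
| 7 days | 1.00% | 2.00% | 1.0 point | 0.70 | 2.0 |
| 45 days | 3.71% | 4.71% | 1.0 point | 1.16 | 1.3 |

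The difference does not move; its standard error grows and the ratio shrinks. Strictly, a subject with ideation in both periods counts once. In the last row the pre-dose risk is 0.005 × 45/7 = 3.2%, so the difference would be 1.0 × (1 − 0.032) = 0.97 points, a negligible change.

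**The case against.** Four answers deserve weight.

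1. The comparison between arms is sound. Waiting and the decision to dose take place under the blind and before exposure, so pre-dose events are balanced in expectation. SAP 4.9.7 reports percentages by category, with no ratio and no test. This stands. A reader might infer that a drug signal is biased towards no difference, but that is true only of a ratio the SAP does not report.

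2. No output is titled treatment-emergent. The phrase describes the instrument, and Table 14.5.4 shows change from the randomization baseline, which is a coherent on-study comparison. This also stands. What remains wrong is the on-treatment flag in the listings, together with a table that cannot be read as post-dose change.

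3. Serious cases are caught elsewhere. Under Protocol 6.2.5, if the investigator judges a subject at risk of suicide or self-harm, the event is recorded as an AE or SAE, and AEs are classed by their own start date. This is partial cover: the protocol does not require an AE for every non-zero score.

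4. The paper S-STS form is not in the documents and may already carry dates for some items. That is possible. Even so, the SAP's rule would not use them.

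**Conclusion.** The on-treatment rule is wrong as written for the S-STS; severity is minor. That conclusion needs no assumed rate. It follows from a recall period that starts at randomization, a dose that can come up to 45 days later, and a flag based on collection time.

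The upper limit on the pre-dose share, 87% with a day-7 visit, comes from the visit schedule alone. The 29% to 53% average over eligible attack rates rests on the exponential wait, on treating the first qualifying attack and on a day-7 visit. An earlier visit raises it and a later one lowers it. A reader might infer that the window lies mostly before the dose. The documents do not fix that: it fits infrequent attacks but not frequent ones.

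The consequence is misclassification of individual events and extra noise in both arms, with the expected difference in percentages essentially unchanged. The endpoint is exploratory and untested, and non-zero scores should be rare.

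**What to change.** Keep the present recall period, so that no interval after randomization goes unassessed. Limiting the End of Treatment score to the time since dosing would lose ideation that resolved before the dose: it would score 0, and a timing question asked only about positive items would never be reached.

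- **Form and Table 1, footnote 8:** for each End of Treatment item scored above 0 in a dosed subject, record whether it was present before the dose, after the dose or both.
- **SAP 4.9.3:** remove suicidal ideation and behaviors from the collection-time definition of on-treatment and call the End of Treatment value on-study.
- **SAP 4.9.7:** classify positive items by the recorded timing, summarize post-dose events alongside the existing Table 14.5.4, and list pre-dose events separately.

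The cost is one timing entry per positive item on a paper form that the clinician already administers, plus a few sentences in the SAP. The drawback is that subjects must place an event before or after their dose from memory. If the form cannot be changed, labelling the End of Treatment S-STS on-study only is an SAP wording edit that removes the false label, though it does not recover the timing.
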